1.1 Assessment and management of risk

Noninvasive transcranial direct current stimulation (tDCS) has been used in human for decades. These noninvasive current stimulation techniques use battery-powered current generator devices that have a built-in circuitry to limit the current above a certain level, typically 2 mA.

The most common **adverse events** are mild skin redness (54%) at the site of the electrodes, which resolves following stimulation, itching (39%) and tingling (22%), followed by headache (16%), discomfort (13%) and burning sensation (10%) (Brunoni et al., 2011, Sampaio-Junior et al., 2018). There is no significant difference in rates between active and sham tDCS, except for skin redness which is more common with active (54%) relative to sham tDCS (19%) (Sampaio-Junior et al., 2018). Participants have been unable to distinguish whether they were receiving active or sham tDCS though, and there have been no differences in the discontinuation rates for active and sham treatments, mean rates 10% and 12%, respectively (Meron et al., 2015). In our recent pilot study in unipolar depression, the discontinuation rate has been 7.6% (2 out of 26 enrolled participants).

The **risk of treatment-emergent mania or hypomania** is estimated to be around 4% with a course of active tDCS and 0.5% with sham tDCS, with no statistical difference between active and sham tDCS (Brunoni et al., 2017; Sampaio-Junior et al., 2018). While the rate is lower than the 5-9% risk associated with antidepressant medication, it might be higher than the risk of <1% associated with repetitive transcranial magnetic stimulation (Xia et al., 2008).

Protocols in human trials (≤ 40 min, ≤ 4 milliamperes, ≤ 7.2 Coulombs) have not produced any reports of serious adverse effect or irreversible injury with over 33,200 sessions and 1,000 participants with repeated sessions (Bikson et al., 2016).

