2.6 Exploratory endpoints/outcomes

Exploratory measures:

- i. Trained rater measure of depressive symptoms: Montgomery–Åsberg Depression Rating Scale (MADRS) remission rate
- ii. Self-report measure of depressive symptoms: Patient Health Questionnaire (PHQ-9)
- iii. Trained rater measure of anxiety symptoms: Hamilton Anxiety Scale (HAMA)
- iv. Trained rater measure of manic symptoms: Young Mania Rating Scale (YMRS)
- v. Self-report measure of disability and impairment: Sheehan Disability Scale (SDS)
- vi. Self-report Quality of Life Enjoyment and Satisfaction Questionnaire (Q-LES-Q)
- vii. Self-report acceptability of tDCS from healthy controls.
- viii. EEG recordings will be acquired during an eyes-closed resting state for 10 minutes and eyes open resting state for 10 minutes using a mobile EEG device in participants' homes (Muse EEG; <https://choosemuse.com/>) (Hashemi et al., 2016). Resting state EEG will be acquired at baseline for healthy controls and at 2 timepoints for participants with bipolar depression: 1) at baseline, and 2) at the end of the 6-week course of treatment. EEG coherence, a measure of neural connectivity, will be examined as a potential surrogate outcome measure (Minuissi et al., 2012).
- ix. Neuropsychological measures: verbal learning (Rey Auditory Verbal Learning Test (RAVLT)) and information processing speed (Symbol-Digit Modalities Test (SDMT)) will be assessed in participants' homes. Neuropsychological assessments will be delivered to participants and administered by a research team member via video call. Our pilot data indicates feasibility and acceptance of the neuropsychological assessments as all participants had completed the assessments (26 out of 26 participants). The measures will be acquired at baseline for healthy controls, and at 2 timepoints for participants with bipolar depression: 1) at baseline, and 2) at the end of the 6-week course of treatment.

Exploratory outcomes:

- 1) MADRS score ≤ 9 following the course of tDCS
- 2) Improvement in self-reported depressive symptoms as measured by PHQ-9
- 3) Improvement in anxiety symptoms as measured by HAMA
- 4) No significant increase in manic symptoms as measured by YMRS score >13
- 5) Improvement in disability experience as measured by SDS
- 6) Improvement in quality of life as measured by Q-LES-Q
- 7) Healthy control participant baseline acceptability questionnaire.

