6.10 Withdrawal criteria

Participants will be withdrawn from the trial if they do not comply with the intervention, namely if they are unable to have a minimum of 50% of the tDCS session (10 out of 21 sessions), or if they develop serious adverse effects from any part of the study. Recording of the reasons for withdrawal will be made. Should a participant lose capacity to consent during the study then they would be withdrawn from the study, and that their identifiable data already collected with consent would be retained for use, and that no further data collection would take place. Their GP will be informed about their withdrawal, and there will have a telephone follow up at 1 month following their withdrawal.

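### The only mania-specific outcome rests on scheduled YMRS ratings with last observation carried forward, so a switch that ends participation can be classed as not above 13

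*Combined protocol and SAP*

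**What the plan says.** **Outcome.** Section 2.6, exploratory outcome 4, reads: "No significant increase in manic symptoms as measured by YMRS score >13". No other outcome in the plan is specific to mania. Section 9.3 gives no analysis, rate or denominator for it.

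**Ratings.** The schedule of events (section 11) marks the YMRS at the start of treatment, once mid-course, at the end of treatment and at the 3-month follow-up. The table is broken in the text available, so the exact columns are approximate. No YMRS is tied to withdrawal or to suspected mania.

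**Withdrawal.** Section 6.10 withdraws participants for low session attendance "or if they develop serious adverse effects from any part of the study". It adds: "Should a participant lose capacity to consent during the study then they would be withdrawn from the study". In that case data already collected are kept and "no further data collection would take place". The same section says "Recording of the reasons for withdrawal will be made" and "there will have a telephone follow up at 1 month following their withdrawal".

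**Missing data.** Section 9.8 applies last observation carried forward (LOCF) to all missing data. Section 5.1.2 excludes anyone with a YMRS above 8.

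**Other records.** Adverse events are checked at sessions and at follow-up (8.4) and recorded for 3 months after the last stimulation (8.9). Serious events go into the CRF and database (8.3). Section 9.3.3 counts adverse events by severity and relatedness, with no mania category.

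**Risk.** Section 1.1 gives treatment-emergent mania and hypomania a paragraph of their own. The risk "is estimated to be around 4% with a course of active tDCS and 0.5% with sham tDCS".

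**The concern.** The event that the outcome is meant to detect can remove the rating that would detect it. Severe mania can plausibly cost a participant capacity or count as a serious adverse effect. Either leads to withdrawal, and the next scheduled YMRS may then never be taken. LOCF fills the gap with a score from before the switch. The missingness depends on the outcome, and the error runs in one direction, towards fewer cases.

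Safety is a secondary objective (2.2), and section 1 says the results will inform the design of a sham-controlled trial. With about two events expected, one misclassified participant halves the estimate. The trial could report that nobody exceeded 13 on the YMRS while a manic serious adverse event sits, unlabelled, in a general severity count.

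**Working it through.** **1. Denominator.** The plan gives no sample size or precision for mania. Its enrolment figure reproduces: 45 / (1 − 0.10) = 50. Outcome 4 has no stated denominator, so I use all 50 enrolled bipolar participants, in line with the primary analysis in 9.3.2.

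**2. What the plan does with a switch that ends participation before the next rating**

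| Last rating before the switch | Score carried forward | Classed as |
|---|---|---|
| Start of treatment | at most 8 (5.1.2) | not above 13 |
| Mid-course | the mid-course score | not above 13, unless it already exceeded 13 |
| End of treatment | the end-of-treatment score | not above 13, unless it already exceeded 13 |

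**3. Expected cases.** 0.04 × 50 = 2.0. The chance of at least one is 1 − 0.96^50 = 0.87.

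**4. Effect of losing cases** (exact Clopper-Pearson 95% intervals)

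| Cases lost | Reported | 95% CI |
|---|---|---|
| 0 | 2/50 = 4% | 0.5% to 13.7% |
| 1 | 1/50 = 2% | 0.05% to 10.6% |
| 2 (worst case) | 0/50 = 0% | 0% to 7.1% |

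Check of the last row: 1 − 0.025^(1/50) = 0.071.

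**5. Chance that the outcome shows no mania at all.** With true rate p and a share m of switches missed, this is (1 − p(1 − m))^50. Only p = 4% comes from the documents. The other rates and all values of m are assumptions.

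| p | m = 0 | m = 0.25 | m = 0.50 | m = 0.75 |
|---|---|---|---|---|
| 2% | 0.36 | 0.47 | 0.61 | 0.78 |
| 4% | 0.13 | 0.22 | 0.36 | 0.61 |
| 8% | 0.02 | 0.05 | 0.13 | 0.36 |

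At 4%, missing half the switches raises the chance of a blank result from 0.13 to 0.36.

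**6. A figure not used.** The last two ratings are 126 − 39 = 87 days apart by the schedule. That gap falls after treatment, whereas section 1.1 states the 4% for a course of stimulation, so the two should not be combined.

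**The case against.** The strongest reply is that the trial does capture mania by other routes. A research assistant monitors every session for adverse events (7.11), adverse events are recorded for 3 months after the last session, serious events are entered in the database, and withdrawal reasons are recorded. A severe switch would enter the adverse event counts in 9.3.3, which belong to a secondary objective and so rank above exploratory outcome 4. This is right, and it rules out several stronger readings that a reader might infer:

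- *Mania is ascertained only by YMRS.* The documents do not support this. Only the mania-specific outcome depends on the YMRS alone.
- *Withdrawn participants have no YMRS.* A baseline rating exists, and a mid-course rating may exist and may already exceed 13. What can be missing is a rating at or after the switch.
- *The plan scores these participants as free of mania.* No section says so. It follows from LOCF in 9.8, and only when the last score is 13 or below.
- *All data stop after any of these withdrawals.* The stop in 6.10 is worded for loss of capacity. Withdrawal for a serious adverse effect carries no such statement, though no section says that YMRS ratings continue.
- *0/50 is the likely result.* It is a bound. The 4% covers hypomania as well as mania, and the documents do not equate hypomania with loss of capacity or with a serious adverse effect.

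The reply does not remove the gap between the records and the outcome. The adverse event and withdrawal records may hold the case, but the analysis does not read them for mania, and the severity count does not label it.

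**Conclusion.** The concern holds for the mania outcome as defined, not for the trial's safety recording as a whole. Applied as written, sections 2.6, 6.10 and 9.8 can class a participant known to have switched as not above 13, and the resulting bias is towards zero. Its size depends on the share of switches that end participation before a rating, which the documents do not give. At the protocol's 4%, one lost case turns 4% into 2%, and losing both is the limit.

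This rests on three assumptions: that the 4% applies to these 50 participants, that the outcome would be reported over all enrolled, and that LOCF in 9.8 covers exploratory outcomes, as its general wording implies. The outcome is exploratory and the primary analysis is unaffected. The change is still worth making, because it draws mainly on data already recorded and removes a one-directional error from a safety result.

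**What to change.** 1. **Sections 2.6 (outcome 4) and 9.3.3.** Count a participant as having treatment-emergent mania or hypomania if any of these holds: a YMRS above 13 at any post-baseline rating; an adverse event or serious adverse event of mania, hypomania or mixed state; or a recorded withdrawal reason of one of these. Report the number over all enrolled bipolar participants with an exact 95% CI.
2. **Section 9.8.** Exempt this outcome from LOCF. Add a sensitivity analysis that counts participants with no later rating as cases. It is a bound: if the 50 − 45 = 5 planned non-completers all lacked a later rating, it would add at most 5/50 = 10 percentage points, before any further loss at follow-up.
3. **Sections 6.10 and 8.9.** Reconcile three statements: that data collection ends after loss of capacity, that a telephone contact follows 1 month after withdrawal, and that adverse events are recorded for 3 months after the last stimulation. As they stand, it is unclear which adverse event records will exist for the participants at issue, and item 1 depends on them.

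**Cost.** Items 1 and 2 are changes to the analysis text and need no new assessments. Adverse event terms and withdrawal reasons must be classified as manic, hypomanic or mixed, and the documents give no criterion for this, so one has to be written. The reported mania rate may be slightly higher.

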6.11 Storage and analysis of clinical samples: N/A

6.12 End of trial: N/A

7 TRIAL TREATMENTS

7.1 Name and description of intervention(s) under investigation

We will use the Flow Neuroscience Flow tDCS device (Figure 1). The tDCS device consists of two electrodes through which the stimulation is applied (anode electrode) and through which the stimulation is returned (cathode electrode), which creates a circuit.

The Flow tDCS device consists of an adjustable headset with the tDCS electrodes built in.

Figure 2. Flow tDCS device

[figure not shown]
7.2 Regulatory status of the drug (if applicable): N/A

7.3 Product Characteristics:

The Flow tDCS device has CE mark approval for the treatment of major depression. The device is portable and commercially available. The device can be programmed to provide the specific stimulation parameters for the study.

The Soterix tDCS device is a similar device which has CE mark approval for the treatment of major depression (Figure 3).

Figure 3. Soterix tDCS device

7.4 Drug storage and supply (if applicable): N/A

7.5 Preparation and labelling of Investigational Medicinal Product (if applicable): N/A

7.6 Dosage schedules:

The Flow Neuroscience tDCS headset will be delivered to the participant's home. The device is designed and approved (CE) to be used at home without supervision.

6-week course of active tDCS treatment, consisting of 5 sessions per week for the first 3 weeks followed by 2 sessions per week for 3 weeks, for a total of 21 tDCS sessions. Duration of each session is 30 minutes. We will use the Flow Neuroscience tDCS device (Figure 1) with a bifrontal montage: anode at left dorsolateral prefrontal cortex (DLPFC) and cathode at right DLPFC (EEG positions F3 and F4, respectively). Stimulation is 2 mA, and electrode area is 35 cm². During each session, participant will be seated comfortably with their eyes open, and research assistant will provide a discreet presence without interacting with the participant by video call.

tDCS parameters are based on meta-analyses (Meron et al., 2015; Dondé et al., 2017; Mutz et al., 2018) indicating that effects are greatest at 2 mA current of 30-minute stimulus. The tDCS equipment records the duration of each session, and there is an automatic shut-off to prevent unsafe use.

7.7 Dosage modifications: N/A

7.8 Known drug reactions and interaction with other therapies: N/A

7.9 Concomitant medication

Participants who wish to begin another antidepressant treatment while taking part in the study will be able to continue in the trial.

7.10 Trial restrictions

There are no known contraindications whilst on the active phase of the trial including dietary requirements or restrictions.

7.11 Assessment of compliance with treatment

The tDCS device records the duration of each session, and there is an automatic shut-off to prevent unsafe use. The equipment will be programmed to provide only the type of stimulation, intensity and session length that are specified in the protocol. The placement is determined by the location of the electrodes which are fitted to the headset. The research assistant will be present at each session, in person or via video link, in order to aid in the initial positioning and to monitor for any adverse events.

7.12 Name and description of each Non-Investigational Medicinal Product (NIMP): N/A

8 RECORDING AND REPORTING OF ADVERSE EVENTS

8.1 Definitions

Term	Definition
Adverse Event (AE)	Any untoward medical occurrence in a participant to whom an intervention has been administered, including occurrences which are not necessarily caused by or related to the intervention.
Adverse Reaction (AR)	An untoward and unintended response in a participant to an intervention which is related to any dose administered to that participant.

	
The phrase "response to an intervention" means that a causal relationship between an intervention and an AE is at least a reasonable possibility, i.e. the relationship cannot be ruled out.
 
All cases judged by either the reporting medically qualified professional or the Sponsor as having a reasonable suspected causal relationship to the intervention qualify as adverse reactions.

Serious Adverse Event (SAE)	
A serious adverse event is any untoward medical occurrence that:
 
 • results in death • is life-threatening • requires inpatient hospitalisation or prolongation of existing hospitalisation • results in persistent or significant disability/incapacity • consists of a congenital anomaly or birth defect 
Other 'important medical events' may also be considered serious if they jeopardise the participant or require an intervention to prevent one of the above consequences.
 
NOTE: The term "life-threatening" in the definition of "serious" refers to an event in which the participant was at risk of death at the time of the event; it does not refer to an event which hypothetically might have caused death if it were more severe.

Serious Adverse Reaction (SAR)	An adverse event that is both serious and, in the opinion of the reporting Investigator, believed with reasonable probability to be due to the trial intervention, based on the information provided.
Suspected Unexpected Serious Adverse Reaction (SUSAR)	A serious adverse reaction, the nature and severity of which is not consistent with the information about the intervention.

NB: to avoid confusion or misunderstanding of the difference between the terms "serious" and "severe", the following note of clarification is provided: "Severe" is often used to describe intensity of a specific event, which may be of relatively minor medical significance. "Seriousness" is the regulatory definition supplied above.

Detailed guidance can be found here:

http://ec.europa.eu/health/files/eudralex/vol-10/2011_c172_01/2011_c172_01_en.pdf

8.2 Operational definitions for (S)AEs

An SAE is any AE from this study that results in one of the following outcomes:

- death
- initial or prolonged inpatient hospitalization
- a life-threatening experience (that is, immediate risk of dying)
- persistent or significant disability/incapacity
- congenital anomaly/birth defect
- considered significant by the investigator for any other reason

Important medical events that may not result in death, be life-threatening, or require hospitalization may be considered serious adverse events when, based upon appropriate medical judgment, they may jeopardize the patient or subject and may require medical or surgical intervention to prevent one of the outcomes listed in this definition.

In all cases AEs and / or laboratory abnormalities that are critical to the safety evaluation of the participant must be reported to the Sponsor; these may be volunteered by the participant, discovered by the investigator questioning or detected through laboratory test or other investigation. Where certain AEs are not required to be reported to the Sponsor, these will still be recorded in the participant's medical records.

8.3 Recording and reporting of SAEs, SARs AND SUSARs

All serious adverse events will be recorded in the CRF as well as in the trial database, from which a line listing of SAEs can be extracted for review. The line-listing of SAEs will be reported to the Sponsor once per year.

All SAEs must be recorded on a serious adverse event (SAE) form. The CI/PI or designated individual will complete the Sponsor's SAE form and the form will be preferably emailed to the Sponsor within 5 working days of becoming aware of the event. The Chief or Principal Investigator will respond to any SAE queries raised by the Sponsor as soon as possible.

Where the event is unexpected and thought to be related to the intervention, this must be reported by the Investigator to the Health Research Authority within 15 days.

For each SAEs the following information will be collected:

- full details in medical terms and case description
- event duration (start and end dates, if applicable)
- action taken
- outcome
- seriousness criteria
- causality (i.e. relatedness to intervention), in the opinion of the investigator
- whether the event would be considered anticipated

8.4 Responsibilities

Principal Investigator (PI):

Checking for AEs and ARs when participants attend for tDCS sessions and at follow up.

1. Using medical judgement in assigning seriousness and causality and providing an opinion on whether the event/reaction was anticipated.
2. Ensuring that all SAEs are recorded and reported to the Sponsor.
3. Ensuring that AEs and ARs are recorded and reported to the Sponsor in line with the requirements of the protocol.

Chief Investigator (CI) / delegate:

1. Clinical oversight of the safety of patients participating in the trial, including an ongoing review of the risk / benefit.
2. Using medical judgement in assigning the SAEs seriousness, causality and whether the event was anticipated where it has not been possible to obtain local medical assessment.
3. Immediate review of all SUSARs.
4. Review of specific SAEs and SARs in accordance with the trial risk assessment and protocol.

Sponsor: (NB where relevant these can be delegated to CI)

1. Central data collection and verification of AEs, ARs, SAEs, SARs and SUSARs according to the trial protocol onto a database.
2. Reporting safety information to the CI, delegate or independent clinical reviewer for the ongoing assessment of the risk / benefit.

3. Notifying Investigators of SUSARs that occur within the trial.

8.5 Notification of deaths

All deaths, including deaths deemed unrelated to the study, will be reported to the Sponsor within 24 hours of notification.

8.6 Pregnancy reporting

All pregnancies within the trial (either the trial participant or the participant's partner, with participants consent) will be reported to the Principal Investigator and the Sponsor.

Pregnancy is not considered an AE unless a negative or consequential outcome is recorded for the mother or child/foetus. If the outcome meets the serious criteria, this would be considered an SAE.

8.7 Overdose: N/A

8.8 Reporting urgent safety measures

If any urgent safety measures are taken the Sponsor shall immediately and in any event no later than 3 days from the date the measures are taken, give written notice to the relevant REC of the measures taken and the circumstances giving rise to those measures.

8.9 The type and duration of the follow-up of participants after adverse reactions.

For 3 months after the last tDCS to the participants, adverse events and reactions be recorded and reported.

Any SUSAR will need to be reported to the Sponsor irrespective of how long after the reaction has occurred until resolved.

